5.2.2 Secondary endpoints

The secondary outcomes:

1. Time to insulin initiation and insulin dose required
2. Maternal morbidity at delivery (hypertensive disorders, antepartum and postpartum haemorrhage)
3. Mode of delivery
4. Gestational age at delivery
5. Postpartum glucose status, insulin resistance, and metabolic syndrome

EMERGE NUIG-2016-01, Statistical Analysis Plan Version 1, 21/03/2023

6. Postpartum BMI, gestational weight gain, and waist circumference
7. Infant birth weight
8. Infant size (large/small/appropriate for gestational age)
9. Neonatal height and head circumference at delivery
10. Neonatal morbidities (Need for neonatal care unit, respiratory distress, jaundice, congenital anomalies, Apgar score)
11. Neonatal hypoglycaemia (defined as plasma glucose <2.6mmol/L on one or more occasions starting 30-60 minutes after birth)
12. Cost effectiveness and budget impact of metformin treatment in addition to usual care
13. Treatment acceptability (Diabetes Treatment Satisfaction Questionnaire DTSQ and Rowan questionnaires)
14. Glycemic control, measured by participant glucocometer.

Quality of Life determined by EQ5D-5L questionnaire

5.3 Derived Variables

Sex-specific birth weight-for-gestational age centiles will be calculated according to Norris et al (2018) in order to determine the proportions of large/small/appropriate for gestational age babies.

6 Study Methods

6.1 General Study design and Plan

The EMERGE study is a phase III, parallel, randomised double-blind, placebo-controlled, trial of metformin (in addition to usual care) versus usual care in 550 women with Gestational Diabetes Mellitus (GDM) across 2 sites in Ireland, followed until 12 weeks post-partum (+/- 4 weeks).

It will comprise 3 steps; 1) screening, 2) treatment, and 3) follow up. Eligible women will be randomised to one of two groups; treatment group or placebo group.

Women randomised to the metformin group will receive metformin 500mg Once Daily (OD), with the dose titrated upwards every 2 days over 10 days increasing to a maximum of 2500mg metformin daily (5 tablets) or maximum tolerated dose, in addition to usual care (exercise and MNT), and taken until delivery.

Participants randomised to the placebo group will receive 1 placebo tablet OD, with the dose titrated upwards every 2 days over 10 days increasing to a maximum

[figure not shown]
EMERGE NUIG-2016-01, Statistical Analysis Plan Version 1, 21/03/2023

of five placebo tablets daily, in addition to usual care (exercise and MNT), and taken until delivery.

Participants will be followed up at 4 (+/- 7days) and 12 weeks (+/- 4 weeks) post-partum for additional maternal and neonatal outcomes.

The control and metformin groups will receive usual care, which consists of medical nutritional therapy (MNT) and information on exercise provided by the Diabetes team. The Diabetes team or trained delegate will instruct women on using a glucometer, and the women will perform 7-point glucose testing before and 1 hour after meals and before bed. Women will be supported by telephone contact from the Diabetes team or trained delegate weekly throughout gestation and attend at 2-4 weekly intervals at an antenatal/diabetes clinic. Usual care is outlined in more detail in section 9.1.1 of the protocol.

EMERGE NUIG-2016-01, Statistical Analysis Plan Version 1, 21/03/2023

6.2 General Study Population

The population for the trial is pregnant women between the ages of 18-50 years, with a diagnosis of GDM between 24-28 weeks gestation (+ 6 days).

EMERGE NUIG-2016-01, Statistical Analysis Plan Version 1, 21/03/2023

Women diagnosed using a 75g Oral Glucose Tolerance Test (OGTT) and International Association of Diabetes in Pregnancy Study Groups (IADPSG) criteria for diagnosis will be eligible to be enrolled in the study. Eligible women must be resident and intend to deliver within the selected trial sites. They must also fulfil all of the Inclusion criteria and none of the Exclusion criteria of the EMERGE Protocol. The geographical area and study population include women from urban and rural locations and women in public and private health care.

6.3 Randomisation and Blinding

Participants will be randomly assigned to receive either metformin or placebo in a 1:1 ratio. Random permuted blocks will be used to ensure similar numbers of participants in each intervention arm throughout the trial and equal numbers in each arm by the end of the study. A minimisation strategy will be used; allowing equal numbers of women with a BMI $\leq/ > 30$ and a history of GDM to be distributed between groups.

A web-based randomisation system will allow participating sites to login and obtain allocated treatment numbers and participant IDs after confirming eligibility through inclusion and exclusion criteria. The treatment number will correspond to a treatment kit at the site. This centralised system will ensure allocation concealment; preventing trial staff from knowing which treatment group will be allocated. Blocks of varying length will also be used to reduce the predictability of the allocation sequence

This trial will be conducted in a double-blind fashion with a placebo control identical to metformin tablets to avoid bias in assessing outcomes. Site Investigators, site personnel, participants, and outcome assessors will be blinded to treatment allocation.

In the case of an emergency, when knowledge of the participants's study treatment assignment is essential for the clinical management of the participant, an investigator may un-blind a participant. Any intentional or unintentional breaking of the blind will be recorded and reported to the sponsor as soon as possible.

7 Sample Size

Our sample size for testing this hypothesis is based on the following; a) 35% of women will require insulin in the control arm, based on information from the MiG trial and data from University Hospital Galway and University Hospital Cork; b) ability to detect a minimum of 33% relative risk reduction in the proportion of women requiring insulin in the experimental (metformin) group (40% to 28% absolute reduction; in the MiG trial only 40% of women on metformin required insulin); c) significance level of 0.05 and 80% power; d) drop-out rate of 5% or less; and e) non-adherence rate of 8% in metformin group. Based on these assumptions, we require a total of 550 participants. This sample size will also have 80% power to demonstrate a difference between the proportions of 12% or more (i.e. a reduction from 60-48%) in the secondary outcome of excessive GWG.

EMERGE NUIG-2016-01, Statistical Analysis Plan Version 1, 21/03/2023

There are 13,000 deliveries annually in both sites. From ATLANTIC DIP 1 we have identified a prevalence of 12.4% for GDM using IADPSG criteria. In our previous universal screening project, we had a consent rate of 75% but a testing rate of circa 50%. In a second study examining uptake rates in primary v secondary care, the screening uptake rate was 88% for screening in secondary care. With universal screening, we expect to pick up 1,560 pregnancies with GDM annually. There is a greater concern with loss to follow-up for the secondary outcome of baseline to post-partum weight change, as post-pregnancy follow-up rates have been reported in some studies to be less than 70%. For this outcome, even with a loss-to follow-up of 50% the resulting 138 per arm will have 80% power, at the 0.05 significance level, to detect a minimum difference in mean weight change of 1.36kgs (assuming a standard deviation of the change in weight of 4kgs). However, every effort will be made to achieve follow-up rates of >95% for post-partum follow-up, and we will implement several strategies to enhance follow-up for this outcome (e.g. home monitoring of weight).

8 ***Timing of analyses***

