501 slightly better than insulin with glyburide inferior to both treatments (Balsells 2015). In the USA
502 analysis of glyburide compared to insulin for treatment of GDM found glyburide to be associated with
503 an increase in adverse perinatal outcomes (Castillo 2015).

504

505 **6.1.6. Limitations of Insulin Therapy**

506

507 Insulin therapy administered by injection is associated with an increased risk of maternal
508 hypoglycaemia, excess maternal weight gain and increased risk of operative delivery (Egan 2013). In
509 addition, the excess weight gain, associated with insulin use, increases insulin requirements further.
510 Furthermore, 40% of women have an extended period (2-4 weeks) of possible hyperglycaemia
511 between initiation of MNT and exercise and introduction of insulin therapy. This may predispose to
512 sub optimal glycaemic control, which is associated with an increased risk of hypoglycaemia in the

513 infant following delivery. Gestational weight gain (GWG) is defined by the American Institute of
514 Medicine (IOM) according to the woman's booking BMI. Excessive GWG is gaining momentum as an
515 additional independent risk factor contributing to a higher odds ratio of development of macrosomia
516 and LGA. We recently carried out analysis of the Atlantic DIP dataset to determine how many women
517 exceeded the IOM guidelines for appropriate weight gain in pregnancy and whether excessive GWG
518 was associated with a further increase in adverse outcomes in pregnancies already at risk. We found
519 that excessive GWG occurred in > 60% of women with GDM. Excessive GWG defined by IOM
520 guidelines further increased the odds ratio of LGA (aOR 2.008; CI 1.241 to 3.248) and macrosomia
521 (aOR 2.166; CI 1.321 to 3.550) significantly on a multivariate analysis when all other contributing
522 variables were adjusted for (Egan 2013). Treatment with insulin further increased the adjusted odds
523 for LGA (aOR 2.802; CI 1.231 to 6.379). Excessive GWG in women with GDM also increased OR of
524 pregnancy induced hypertension (aOR 1.719; CI 1.037 to 2.852). This suggests that a focus on
525 minimising excessive GWG is important and opens the debate regarding the usefulness and
526 effectiveness of insulin as the preferred treatment modality in women where MNT fails.
527

528 6.1.7. Metformin use for GDM

529
530 In many European countries oral hypoglycaemic agents (e.g. metformin or glyburide) are used for

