811 is up to 28 weeks (+6 days) gestation, which can occur on the same day as screening or up to 7 days
812 post-screening.
813

814 Participants at all trial sites will also be invited to partake in a bio-banking sub-study which involves
815 obtaining maternal blood samples at randomisation and gestational age 38 weeks (+/- 1 week) and
816 also a cord blood sample at delivery. This is executed under a separate Ethics Committee approved
817 protocol and is executed as guided by local practice patterns and the availability of resources
818 (including staff).
819

820 Once the participant has been randomised, additional data collected will include:
821

822 1. Physical measurements and vital signs (heart rate, BP, height, weight)
823 2. Demographics (date of birth (DOB), race)

824 3. Social history (smoking and alcohol)
825 4. Socioeconomic status
826 5. Baseline gastrointestinal symptoms
827 6. EQ5D-5L Questionnaire
828 7. Laboratory tests (see section 8.4.5)
829 8. Medical resources used since diagnosis of pregnancy
830 9. Usual care received

831
832 The participant will then be dispensed study medication and administration instructions. The pack
833 numbers of dispensed medication will be documented on the dispensation log.

834
835 **8.3.2. Prenatal Visit and Procedures**

836
837 Prenatal visits will occur approximately every 2 weeks post randomisation in line with routine
838 antenatal clinic visits. Visits that do not require an in person physical measurement, laboratory
839 assessment or drug dispensation can be completed over the telephone. The following data will be
840 collected and procedures will be performed:

841
842 1. Gestational age in weeks
843 2. Review of concomitant medications
844 3. Review of insulin requirements
845 4. Review of adverse events
846 5. Gastrointestinal symptom review
847 6. Review of hypoglycaemic events
848 7. Review of medical resources used
849 8. Glucometer data download (at in person visits only, see section 8.4.7.)

850
851 The following data will be collected in addition to the above:

852
853 1. Study drug dispensing (every 4 weeks)
854 2. Physical measurements and vital signs (heart rate, BP and weight to be taken at gestational
855 weeks 32 (+/- 1 week) and 38 (+/- 1 week))
856 3. Usual care received (week 4)
857 4. Laboratory tests (at gestational week 32 (+/- 1 week) AND at gestational week 38 (+/- 1
858 week), see section 8.4.5.)

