- Maternal BMI, waist circumference, maternal gestational weight gain (GWG) blood glucose
- status, insulin resistance status and metabolic syndrome postpartum
- Proportion of infants with morbidities;
- Infant birth weight
- Proportion of maternal morbidities

1828

1829

1830

1831

1832

1833

1834 **11.5.3. Health Economic Outcomes**

1835

1836 Health economic outcomes include:

1837

- EQ5D-5L
- Quality Adjusted Life Years (QALYs)
- Costs of healthcare associated with the intervention and control arms

1838

1839

1840

1841 **11.6. The level of statistical significance**

1842

1843 The level of statistical significance will be set at $\alpha=0.05$ for all analyses i.e. a p-value <0.05 with 95%

1844 CI's not containing zero will be considered statistically significant.

1845

1846 **11.7. Procedure for accounting for missing, unused and spurious data**

1847 An analysis of all missing data will be carried out to identify the likely missing data mechanism (e.g.

1848 missing completely at random, missing at random, and missing not at random). A suitable multiple

1849 imputation strategy will then be employed to determine the sensitivity of missing data on the inference
1850 gleaned from the final model.

1851

1852 11.8. Health economic analysis

1853 The Health Economic and Policy Analysis (HEPA) research team at NUI Galway have previous
1854 experience, within an Irish healthcare context, in the design and conduct of economic evaluation
1855 alongside randomised controlled trials. The health economic analysis will consist of trial-based
1856 economic evaluation and will incorporate both cost effectiveness analysis and cost utility analysis to
1857 compare the alternative treatment strategies: (1) metformin in addition to usual care for GDM (that is,
1858 MNT and/or insulin); and (2) usual care for GDM. The economic evaluation will be undertaken in a
1859 manner consistent with the guidelines issued by Health Information and Quality Authority (HIQA)
1860 (2014) for the evaluation of technologies in Ireland. The basic tasks of the evaluation are to identify,
1861 measure, value and compare the costs and outcomes of the alternatives being considered. Evidence
1862 collected on resource use and clinical outcome measures alongside the trial will provide the basis for
1863 the analysis over the trial follow up period. A healthcare provider perspective will be adopted with

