8.1 Interim analyses

There were no planned interim analyses for this study. However, an analysis was carried before full accrual was completed to reassess some of the assumptions used in the sample size calculations. As a result of this analysis it was observed that the overall proportion of women taking insulin in the study was larger than the one estimated in the original sample size calculations. Based on this information, it was established that a reduced sample of 535 participants would achieve the same 80% power to answer the primary research question. Therefore, the total sample size will be 535.

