13.2 Secondary Efficacy Analyses

Secondary efficacy outcomes include:

- Maternal morbidity at delivery (hypertensive disorders, antepartum and postpartum haemorrhage)
- Mode and time of delivery
- Maternal post-partum BMI, waist circumference, maternal gestational weight gain (GWG) blood glucose status, insulin resistance status and metabolic syndrome postpartum
- Proportion of maternal morbidities
- Infant birth weight
- Infant size (large/small/appropriate for gestational age)
- Neonatal height and head circumference at delivery
- Neonatal morbidities (Need for neonatal care unit, respiratory distress, jaundice, congenital anomalies, Apgar score)
- Neonatal hypoglycaemia (defined as plasma glucose <2.6mmol/L on one or more occasions starting 30-60 minutes after birth)

EMERGE NUIG-2016-01, Statistical Analysis Plan Version 1, 21/03/2023

- Proportion of infants with morbidities
- Treatment acceptability (Diabetes Treatment Satisfaction Questionnaire DTSQ and Rowan questionnaires)
- Quality of Life determined by EQ5D-5L questionnaire

Exploratory analyses based on generalised linear models will be used to estimate the treatment effect for each of the secondary outcomes while adjusting for the stratification variables and relevant baseline characteristics.

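### The stated 80% power for excessive gestational weight gain counts no losses (about 78% at 535 with the plan's 5% drop-out), and the powered yes/no outcome is not carried into the SAP's endpoint and analysis lists

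*SAP*

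**What the plan says.** SAP section 7 and protocol 11.2 build the sample size from the same inputs: "c) significance level of 0.05 and 80% power", drop-out of at most 5%, and 8% non-adherence in the metformin arm. They arrive at 550. Both then add: "This sample size will also have 80% power to demonstrate a difference between the proportions of 12% or more", with the example given as "a reduction from 60-48%) in the secondary outcome of excessive GWG". Neither says whether the drop-out and non-adherence allowances apply to that sentence.

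SAP 8.1 later reduces the trial because insulin use was higher than assumed: "Therefore, the total sample size will be 535". The reason given concerns the primary question only, and the GWG power is not restated.

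Excessive GWG is named as a secondary outcome in the SAP preface (section 3). It appears again in the overall objective (section 5, part b) and as secondary objective 7 (section 5.1.2). The endpoint list (5.2.2, item 6) has gestational weight gain without a threshold. The analysis list in 13.2 reads: "Maternal post-partum BMI, waist circumference, maternal gestational weight gain (GWG) blood glucose status, insulin resistance status and metabolic syndrome postpartum". Section 5.3 (Derived Variables) covers birth-weight centiles only.

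The nearest definition is in the protocol background (6.1.6), where the limits are those of the American Institute of "Medicine (IOM) according to the woman's booking BMI".

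**The concern.** A power statement should describe the number of women expected to be analysed. Here the paragraph sets out its expected losses and then quotes a power that is reached only when nobody is lost. If the trial finds no difference in excessive GWG, readers will weigh that result against a sensitivity the trial does not quite have.

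The second matter is specification. The power sentence is about a proportion, so it needs a yes/no outcome with a threshold, a starting weight and an ending weight. The sections that govern analysis give none of these. The only model written specifically for weight (SAP 13.1) is a linear mixed model for mean change from baseline to post-partum, which is a different quantity. Definition, scale and model would then be left to choose after the data are in.

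**Working it through.** **Inputs**
- Control 60%, metformin 48%, alpha 0.05, 80% target, drop-out of at most 5%, 8% non-adherence on metformin: SAP section 7.
- Totals 550 (SAP section 7) and 535 (SAP 8.1); allocation 1:1 (SAP 6.3).
- Analysis by intention to treat, secondary outcomes included: SAP 9.1.
- Two-sided testing is assumed. The plan does not say so in words, but protocol 11.6 ties significance to 95% confidence intervals. A one-sided test would give 88.2% at 550, which does not match the stated 80%.

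**Formula** (two proportions, pooled variance under the null, n per arm):

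power = Φ{ [ |p1 − p2| − 1.96 √(2 p̄(1 − p̄)/n) ] / √( [p1(1 − p1) + p2(1 − p2)]/n ) }

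For 0.60 v 0.48, p̄ = 0.54, so 2p̄(1 − p̄) = 0.4968 and p1(1 − p1) + p2(1 − p2) = 0.2400 + 0.2496 = 0.4896.

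**Step 1: the plan's figure.** n = 550/2 = 275. The null standard error is √(0.4968/275) = 0.04250 and the alternative one is √(0.4896/275) = 0.04219. The argument is (0.12 − 0.0833)/0.04219 = 0.870, so power is 80.8%. The formula needs 270 per arm (540 in total) for 80%. The stated 80% therefore reproduces at 550, with everyone analysed.

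**Step 2: is 550 before or after losses?** The next paragraph of SAP section 7 takes a 50% loss to follow-up and reaches 138 per arm for post-partum weight change: 0.5 × 275 = 137.5. So the plan treats 550 as the number before loss.

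**Step 3: apply the 5% drop-out.** At 550, n = 550 × 0.95/2 = 261.25. At 535, n = 535 × 0.95/2 = 254.1; the argument is (0.12 − 0.0867)/0.0439 = 0.760, giving 77.6%.

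**Step 4: non-adherence, as an assumption.** Suppose 12 points is the effect under full adherence and the 8% take the control risk. The metformin risk becomes 0.48 + 0.08 × 0.12 = 0.4896, a difference of 0.1104. At n = 254.1 the argument is (0.1104 − 0.0866)/0.0439 = 0.542, giving 70.6%.

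| Total | No loss | 5% drop-out | 5% drop-out and full dilution (assumption) |
|---|---|---|---|
| 550 | 80.8% | 78.7% | 71.8% |
| 535 | 79.7% | 77.6% | 70.6% |

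Reading down a column, the cut to 535 costs about one point. Reading across a row, 5% drop-out costs about two points, and full dilution a further seven. Reaching 80% would need 570 in total with 5% drop-out (270/0.95 is 285 per arm), or 672 with full dilution as well (319/0.95 is 336 per arm).

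Fisher's exact test gives lower values: 79.4% at 550 with no loss, and 77.5%, 74.7% and 67.6% across the 535 row.

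**Step 5: trace the outcome.** The power sentence and objective 7 concern excessive GWG. Protocol 6.1.6 reports it in more than 60% of women with gestational diabetes under the IOM definition, which fits the 60% control assumption. The powered quantity is therefore most plausibly the IOM one. No threshold or binary model for it appears in SAP 5.2.2, 5.3 or 13.2. The weights the protocol lists are taken at randomisation (8.3.1, "Physical measurements and vital signs (heart rate, BP, height, weight"), at gestational weeks 32 and 38 (8.3.2) and at 12 weeks post-partum (8.3.5). Booking weight is not named among them.

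**The case against.** The strongest reply is that the quoted sentence refers to 550, where 80% reproduces, and does not claim to include the losses. Drop-out is given as an upper bound, so 77.6% is the floor from drop-out alone, 2.4 points below nominal. SAP 13.2 calls the secondary analyses exploratory, and the SAP is dated 21/03/2023, after women had already entered in repeat pregnancies. Restating a nominal power that late changes no estimate or interval. All of this is fair and keeps the point modest. It does not make the sentence right, because the paragraph lists the losses and the plan deducts losses for its other weight outcome.

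Four stronger readings are tempting, and the documents do not support them.

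- **That the cut to 535 caused the shortfall.** It accounts for about one point; power with 5% drop-out is already 78.7% at 550.
- **That 71% is the power on the plan's own terms.** The plan does not say that 12 points is a full-adherence effect, or that non-adherers revert to the control risk. If 12 points is already the intention-to-treat difference, power at 535 is 77.6% to 79.7%. Full reversion also fits poorly with SAP 12.4, where non-compliance means under 80% of the maximum tolerated dose. A woman taking 75% of that dose is counted as non-compliant but is still treated.
- **That objective 7 would go unanswered, or that this is the main secondary outcome.** The outcome is named in the preface and objectives, and the generalised linear models of 13.2 can fit a yes/no response. No passage ranks the secondary outcomes.
- **That booking weight is not collected.** The CRF is not among the documents. The current-pregnancy items in protocol 8.3.1 are an open list, and SAP 12.3 summarises current pregnancy at baseline.

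**Conclusion.** The 80% figure is wrong as a description of the planned trial, by a small amount on the plan's stated inputs. It holds only with all 550 analysed (80.8%). With 5% drop-out it is 78.7% at 550 and 77.6% at 535, mainly because losses were not counted. About 71% at 535 is the lower end and depends on the two non-adherence assumptions above. All figures assume a two-sided 5% pooled test and the plan's 60% v 48%.

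The gap in the lists is a real but minor misalignment. An outcome with a stated power and an objective has no threshold, derivation or named model in the sections that direct the analysis. Whether the data needed for the IOM definition are missing cannot be settled from the documents.

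**What to change.** In SAP section 7, and in protocol 11.2 so that the two agree, restate the figure: at 535 with 5% drop-out, power for 60% v 48% is about 78% (about 71% if 8% non-adherence fully dilutes the effect, an assumption).

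Add excessive GWG as a yes/no outcome, judged by the IOM limits for booking BMI as in protocol 6.1.6, to SAP 5.2.2 and 13.2. Put its derivation in 5.3, with the limits and the start and end weights stated. Name the analysis: logistic regression with the stratification factors (BMI and previous gestational diabetes), which falls within the models 13.2 already allows.

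Confirm that the CRF holds booking weight. If it does not, take it from routine antenatal notes.

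The cost is a slightly less favourable power figure, a few lines in the SAP with the matching sentence in the protocol, a CRF check and, at worst, abstraction of one weight per participant. Settle the definition before the unblinded analysis of perinatal outcomes described in SAP 8.2.
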